4. STUDY DESIGN AND ENDPOINTS

4.1 DESCRIPTION OF THE STUDY DESIGN

This is a pilot randomized phase 2 clinical trial to evaluate the efficacy and tolerability of TKI therapy through adaptive (intermittent) versus conventional (continuous) regimen in patients with DTC or MTC. Eligible subjects with DTC or MTC will have measurable disease according to Response Evaluation Criteria in Solid Tumors (RECIST 1.1) and will be randomized 2 to 1 to receive adaptive (intermittent) versus conventional (continuous) therapy when and if the tumor marker drops 50% or more from the baseline level (before initiating TKI treatment) within the first two months of treatment. Randomization will be stratified by cancer types, DTC vs. MTC. Patients in which the tumor marker does not drop by 50% or more within 2 months (“non-responders”) will be kept on conventional therapy and used to compare with the patients who drop their tumor markers by 50% or more as an exploratory analysis.

All patients will start receiving standard of care treatments: Lenvatinib 24 mg daily or Sorafenib 400 mg twice daily with DTC; Cabozantinib 140 mg daily or Vandetanib 300 mg daily with MTC. Doses will be adjusted as needed due to toxicity or drug tolerance in both arms (See section 6.1.8).

- Patients in the conventional therapy regimen (“responders” and non-responders”) will receive continuous (daily) treatment at the indicated dose.

- Patients in the adaptive therapy regimen will receive TKI therapy in cycles: continuous (daily) treatment at the indicated dose until the patients’ tumor marker (thyroglobulin in DTC patients; calcitonin or CEA in MTC patients) drops by $\geq 50\%$ from the level at the time of enrollment (“baseline” level). $\geq 70\%$ of Only tumor markers that meet inclusion criteria at baseline can be used for randomization and adaptive therapy purposes. A new cycle of TKI treatment will begin:

1. When/if the tumor marker increases to $\geq 70\%$ of the “baseline” level.
OR
2. At the discretion of the treating physician, if a patient develops worsening disease-related symptoms with rising tumor marker levels indicating disease progression. In the case of resumption for disease-related symptoms, TKI treatment will continue until the symptoms improve at the discretion of the treating physician and the tumor markers are again $\leq 50\%$ from the level at the time of enrollment.

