7.3.3 FOLLOW-UP

Follow-up Visits

Study participants will be seen weekly for the first cycle (Cycle 1 Days 8, 15 and 22), every two weeks for the second cycle (Cycle 2 Days 1, 15), every four weeks until cycle 12 (Day 1 of Cycles 3-12); and every 2 cycles thereafter until end of study (Day 1 of cycles 14, 16, 18, 20 and 24). However, when the patient is off the TKI with observation only in the adaptive arm, the patient needs to follow up every 28 days (+/- 7 days) for determination of starting a new cycle.

In each scheduled visit we will:

- Obtain vital signs.
- Record all concomitant medication use.
- Perform a comprehensive physical examination.
- Evaluate ECOG performance status.
- Obtain laboratory tests and urinary dipstick.
- Assess for AEs and SAEs.
- Assess compliance with the medication.
- Assess survival.

Thyroid panel evaluation

Thyroid panel will be assessed every 2 weeks during the first two cycles (Cycle 1 Day 15, Cycle 2 Day 1, Cycle 2 Day 15, and Cycle 3 Day 1). If the tumor marker (thyroglobulin in DTC patients; calcitonin or CEA in MTC patients) drops by $\geq 50\%$ from baseline (Cycle 1 Day 1) during the first two cycles (analysis of Cycle 3 Day 1 included), the patient will be randomized to receive either standard (continuous) or adaptive (intermittent) therapy. Patients randomized to

the standard therapy arm will then get Thyroid panel checked every 3 cycles (Day 1 of Cycle 6, 9, 12). Patients randomized to the adaptive therapy arm will get Thyroid panel checked every cycle (Day 1) during the first two years. After 24 months, patients in the adaptive therapy regimen who remain on TKI therapy will be given the choice to continue with the adaptive therapy regimen and monitoring of the thyroid panel in every cycle; or to convert to standard (continuous) regimen in which case thyroid panel evaluation will be checked every 3 cycles. In either case, all patients that continue to receive TKI therapy beyond 24 months will be treated off trial. Patients in which the tumor marker does not drop $\geq 50\%$ within the first two months of TKI therapy will be managed by the standard of care.

Diagnostic imaging

Diagnostic imaging of affected and suspected sites (CT and/or MRI) will be done at Day 1 of cycles 3, 6, 9, 12, 16, 20, 24 in all patients. Diagnostic imaging will continue to be done every 4 months thereafter while the patient remains on TKI therapy or as clinically indicated otherwise.

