7.3.5 EARLY TERMINATION VISIT

An End of Treatment (EOT) visit will be performed for all subjects who do not complete the 24 month treatment period for any reason (e.g. disease progression, unacceptable toxicity, withdraw consent, etc.). At the end of treatment (30 days after last TKI dose, or any time within 30 days of being removed from treatment for patients in the adaptive therapy arm) the following data will be collected:

- Obtain vital signs.
- Record all concomitant medication use.
- Perform a comprehensive physical examination.
- Evaluate ECOG performance status.
- Obtain laboratory tests and urinary dipstick.
- Assess for AEs and SAEs.
- Assess compliance with the medication.

- Assess survival.

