7.3.7 SCHEDULE OF EVENTS TABLE

Table 8. Schedule of events

Phase	Screen	Experimental phase																	
		1	1	1	1	2	2	3	4	5	6	9	12	16	20	24	EOT ⁿ		
Cycle (28 days) ^a	0	1	1	1	1	2	2	3	4	5	6	9	12	16	20	24	EOT ⁿ		
Day ^b	-28 to -0	1	8	15	22	1	15	1	1	1	1	1	1	1	1	1	30		
Assessments																			
Informed consent ^c	X ^d	X ^d																	
Inclusion/exclusion	X ^d	X ^d																	
Randomization		When/if tumor marker drops ≥50% within first 2 cycles ^m																	
Demographic data	X ^d	X ^d																	
pTNM staging ^e	X ^d	X ^d																	
Medical history	X ^d	X ^d																	
ECOG ^f	X ^d	X ^d	X	X	X	X	X	X	Patients on conventional therapy: Q3 cycles (Day 1 of cycles 6, 9, 12, 15, 18, 21, 24)									X	
Vital signs ^g	X ^d	X ^d	X	X	X	X	X	X	Patients in the adaptive therapy: On TKI: Every day 1 of each cycle for up to 12 cycles, Q2 cycles (Day 1 of cycles 14, 16, 18, 20, 22 and 24). Off TKI: Every day 1 of each cycle until resume TKI.									X	
Physical exam	X ^d	X ^d	X	X	X	X	X	X										X	
Laboratory tests ^h	X ^d	X ^d	X	X	X	X	X	X	X	X	X	X	X	X	X	X	X	X	
Urine dipstick	X ^d	X ^d	X	X	X	X	X	X	X	X	X	X	X	X	X	X	X	X	
Thyroid panel ⁱ	X ^d	X ^d		X			X	X	X	Patients on conventional therapy: Q3 cycles (Day 1 of cycles 6, 9, 12, 15, 18, 21, 24) Patients in the adaptive therapy: Day 1 of each cycle									X
Pregnancy test ^l	X ^d	X ^d																	
Imaging studies (CT/MRI) ^k	X ^d	X ^d							X			X	X	X	X	X	X		
Mandatory research blood collection	X								X			X	X	X			X	X	
Tumor collection	Mandatory: - Archival Optional: - Fresh Tissue																	Optional: - Fresh Tissue	
Concomitant meds	X	Throughout																X	
AEs/SAEs ^l		Throughout																X	
Survival		Throughout																X	

- a: Patients in adaptive therapy arm will continue to follow the schedule with TKI withheld as long as their markers continue to be below 70% of the 'baseline' level. Upon resumption of TKI therapy the Cycle number will match that which would be expected based on duration on treatment (ie TKI therapy is omitted, not held).
- b: Efforts should be made to conduct study visits on the day scheduled during the first month (\pm 3 days) and there after \pm 5 days. Clinical laboratory assessments may be conducted anytime within 72 hours prior to the scheduled visit, unless otherwise specified in the Schedule of Visits and Procedures.
- c: Informed consent may be taken up to 8 weeks prior to C1D1.

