10.3 DESCRIPTION OF STATISTICAL METHODS

10.3.1 ANALYSIS OF THE PRIMARY EFFICACY ENDPOINT(S)

The primary endpoint is the time-to-discontinuation of treatment.

- The measurement endpoint is the status of a patient 12 months following the start of TKI.
- This is a binary metric. 1 = the patients is still receiving TKI at 12 months; 0 = patient is no longer on TKI due to cancer progression and/or toxicity.
- The results will be described as % patients that remain on TKI at 12 months by experimental and control groups.
- The test statistic will a Fisher's Exact test on a two by two contingency table of patient counts based on all four combinations of whether a patient remains or does not remain on TKI (0 or 1) by treatment group (adaptive therapy or continuous therapy)
- We will begin by comparing the historical control patients with the control patients of the trial. If these two groups do not differ (using a Type I error rate of $p > 0.1$) then they shall be combined to provide the patient counts for the Fisher's Exact Test comparison of the control group to the experimental group of the trial.
- If the historical control patients differ from the control patients of the trial (using a Type I error rate of $p < 0.1$) then they will be compared separately to the experimental group using Fisher Exact test's with a Bonferroni adjusted Type I error rate of $p < 0.05$.

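### Section 10.3.1 gives no valid 12-month score for an adaptive-arm patient who is on a planned, marker-driven TKI break

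*Combined protocol and SAP*

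**What the plan says.** Section 10.3.1 turns the primary endpoint into a binary status 12 months after TKI start. The coding bullet reads 1 = "the patients is still receiving TKI at 12 months; 0 = patient is no longer on TKI due to cancer progression and/or toxicity". The reporting bullet says "The results will be described as % patients that remain on TKI at 12 months by experimental and control groups". The Fisher bullet forms its table from "whether a patient remains or does not remain on TKI (0 or 1) by treatment group". The last two attach no reason for being off drug.

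Planned breaks are part of the experimental regimen. Section 4.1 states: "Patients in the adaptive therapy regimen will receive TKI therapy in cycles: continuous (daily) treatment at the indicated dose until" the marker has fallen by at least half from baseline; treatment restarts at 70% of baseline or on worsening symptoms with a rising marker. Section 7.3.3 sets visits for the period "when the patient is off the TKI with observation only in the adaptive arm". Footnote a to Table 8 adds: "Patients in adaptive therapy arm will continue to follow the schedule with TKI withheld as long as their markers continue to be below 70" percent of baseline. The conventional arm is treated daily and has no planned break.

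Section 4.2.1 limits discontinuation to progression, intolerability as defined there, or disease-related death. Section 10.4 refers to 4.2.1 for the criteria, adds elective withdrawal as an event, and puts all randomized patients in the primary analysis.

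**The concern.** Randomization requires a marker fall of at least 50%, and the adaptive rule treats until a fall of at least 50%. Adaptive patients therefore meet the break criterion when they are randomized, so a break at month 12 is an ordinary state in that arm. The primary rule has no agreed place for it: the coding bullet leaves the patient unclassified, and the next two bullets imply failure.

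Every affected patient is an event-free patient in the experimental arm. Leaving them out removes successes from one arm; coding them 0 turns successes into failures in one arm. If the question is settled only once data exist, the choice moves the experimental arm alone, in a trial where treatment assignment is known.

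**Working it through.** **The plan's own figure.** Sections 10.1 and 10.4 state 82% power for 24 against 12 patients, medians of 24 and 12 months, 24 months' accrual plus 24 months' minimum follow-up, and one-sided 0.20. With exponential times the event probability is 1 − (e^(−24λ) − e^(−48λ))/(24λ), where λ = ln 2/median. Expected events are 12 × 0.865 = 10.4 and 24 × 0.639 = 15.3, in total 25.7. Power is Φ(ln 2/√(1/10.4 + 1/15.3) − 0.842) = 81%. A log-rank simulation also gives 81%, and 68% at HR 0.6 against the stated 67%. The stated figures therefore reproduce, but they describe a survival comparison and not the 12-month Fisher test.

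**How each rule treats a responder on a break at month 12**

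| Rule | Result |
|---|---|
| 10.3.1 coding bullet | neither 1 nor 0 |
| 10.3.1 percentage and Fisher bullets | not on TKI, so among the failures |
| 4.2.1 | no event |
| 10.4 | must be in the primary analysis |

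**Twelve-month rates at the plan's medians.** Adaptive: s = 2^(−12/24) = 0.707, or 17.0 of 24. Control: 2^(−12/12) = 0.500, or 6 of 12. The gap is 20.7 points.

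**In whole patients.** Suppose 17 adaptive patients are event-free and five of them are on a break. Coded 0: 12/24 = 50%, no gap. Dropped: 12/19 = 63%, a gap of 13 points. Coded 1: 17/24 = 71%, a gap of 21 points.

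**Effect by break share.** Let b be the share of event-free adaptive patients on a break at month 12. The documents give no value, so 0 to 40% is assumed. Coded 0, the adaptive rate is s(1 − b). Dropped, it is s(1 − b)/(1 − sb), with 24(1 − sb) patients left on average. Power is by exact enumeration of Fisher's test, trial controls only, at one-sided 0.20. That level is borrowed from 10.1, because 10.3.1 sets none for the comparison with pooled controls.

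| b | Rate, coded 0 | Power | Rate, dropped | Mean n | Power |
|---|---|---|---|---|---|
| 0% | 70.7% | 52% | 70.7% | 24.0 | 52% |
| 10% | 63.6% | 34% | 68.5% | 22.3 | 46% |
| 20% | 56.6% | 20% | 65.9% | 20.6 | 39% |
| 30% | 49.5% | 10% | 62.8% | 18.9 | 31% |
| 40% | 42.4% | 4.5% | 59.2% | 17.2 | 24% |

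**Share at which the expected benefit vanishes.** Coded 0: s(1 − b) = 0.5 gives b = 1 − 0.5/0.707 = 29%. Dropped: s(1 − b) = 0.5(1 − sb) gives b = (0.707 − 0.5)/(0.5 × 0.707) = 59%. With the plan's 20-month median, s = 2^(−12/20) = 0.660 and the shares are 24% and 48%.

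**Sensitivity.** If the arms differ only from month 2, s = 2^(−2/12) × 2^(−10/24) = 0.667, and the shares become 25% and 50%. Section 10.3.1 may also pool historical controls, whose number is not given. With 24 assumed at a 50% rate and breaks coded 0, power falls from 69% to 27% at b = 20%.

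**The case against.** A reader might infer that 10.3.1, taken literally, counts adaptive responders on a break as failures. The documents do not support that as the settled reading. The coding bullet confines 0 to progression and/or toxicity, and the Fisher bullet refers back to those 0 and 1 codes. The failure reading comes only from the wording of the percentage and Fisher bullets.

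Other text favours remaining on the assigned regimen as the intended meaning. Footnote a numbers cycles after a break as if time on treatment had kept running, and explains that "TKI therapy is omitted, not held". Section 4.1 describes adaptive patients at 24 months as still on TKI therapy without excluding those on a break. Section 4.2.1 predicts longer time on TKI treatment in the adaptive arm, which makes sense only for time on the regimen. Section 7.3.5 times the end-of-treatment visit from the last dose, "or any time within 30 days of being removed from treatment for patients in the adaptive therapy arm", so a break is not the end of treatment there.

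All of this stands, and it makes the likely intention fairly clear. It does not supply the missing rule. Section 7.3.3 calls the same patients off the TKI, and no sentence in 10.3.1 says that a break counts as remaining on treatment. Nor can such patients simply be left unclassified, given 10.4's requirement on the analysis set.

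The size is also open to challenge, since the break share is unknown and the alpha is borrowed. The figures are therefore shown for both readings and over a range.

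**Conclusion.** The concern holds as a defect in the primary scoring rule: a planned break has no valid code, the bullets of 10.3.1 disagree about it, and both outcomes depart from 4.2.1 and 10.4. The direction is certain, because only event-free adaptive patients are affected; either treatment lowers the adaptive rate. The size is not known. At the plan's medians and a 20% break share, power would be 39% (dropped) or 20% (coded 0), against 52% with breaks coded 1. These figures rest on exponential times, an assumed break share, the one-sided 0.20 of 10.1, and trial controls only.

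A reader might go further and conclude that the plan has adopted a failure rule for breaks, or that the larger losses are what to expect. Neither follows: the coding bullet does not make a break a failure, and the documents give no break share.

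It should be corrected before outcomes are tabulated by arm. The conflict between the 2-year endpoint in 4.2.1 and the 12-month test is a separate matter; the event definition below serves whichever time point or test is kept.

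**What to change.** In 10.3.1:

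- Define 0 as a discontinuation event by 12 months: progression, intolerability or disease-related death as 4.2.1 defines them, or elective withdrawal as 10.4 states.
- Define 1 as no such event by 12 months.
- State that an adaptive-arm patient on a planned marker-driven break is coded 1.
- In the percentage and 2x2 bullets, replace the on-TKI wording with free of a discontinuation event.

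The cost is wording only. Sample size, visits, treatment and the roles of the primary and sensitivity analyses do not change. How to code other reasons for stopping, such as unrelated death, loss to follow-up or investigator termination, and which method to use for the censored sensitivity analysis, are separate choices and not part of this fix.

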10. STATISTICAL CONSIDERATIONS

10.1 STATISTICAL AND ANALYTICAL PLANS

This is a randomized phase II clinical trial with 2:1 randomization to adaptive therapy versus conventional therapy. The primary endpoint is time-to-discontinuation (TTD) of treatment, which is a "survival analysis"-type statistical comparison. We plan to enroll 24 patients on the adaptive therapy and 12 on the conventional therapy arm. Assuming uniform enrollment of patients for 2 years, with a minimum follow-up of 2 years, and a one-sided $\alpha = 0.20$, we will have 82% power to detect a hazard ratio of 0.50, assuming 12 and 24 month median TTD for the conventional and adaptive therapy groups. If the median TTD of the adaptive group is 20 months (HR=0.6), the power is 67%.

We anticipate that 20% of the patients will not have the $\geq 50\%$ drop in tumor markers needed for study randomization arm of the study. Thus, we anticipate recruiting ~45 patients to have 36 patients for randomization.

The ~9 patients enrolled to the trial not candidates for the randomization will be given conventional therapy as standard of care. As an exploratory analysis, and realizing that the sample sizes are small, we will compare their PFS rates with the 12 patients from the randomized portion of the trial who receive conventional therapy using the log-rank test.

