10.2 STATISTICAL HYPOTHESES

We hypothesize that we will prolong time to treatment discontinuation with the adaptive therapy regimen (**experimental group**) compared to the continuous therapy regimen (**control group**). Literature suggests that the median time to discontinuation with standard (continuous) therapy is 12 months. We hypothesize that the median time to discontinuation will increase to 24 months (Hazard ratio 0.50) with the adaptive therapy regimen. The power of the study to detect this difference is 82% for an alpha of 0.20.

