10.4 SAMPLE SIZE

The planned study is a randomized clinical trial, with 2:1 randomization to adaptive therapy versus conventional therapy. The primary endpoint is time-to-discontinuation (TTD) of treatment, which is a “survival analysis”-type statistical comparison. We plan to enroll 24 patients on the adaptive therapy and 12 on the conventional therapy arm. Assuming uniform enrollment of patients for 2 years, with a minimum follow-up of 2 years, and a one-sided $\alpha = 0.20$, we will have 82% power to detect a hazard ratio of 0.50, assuming 12 and 24 month median TTD for the conventional and adaptive therapy groups. If the median TTD of the adaptive group is 20 months (HR=0.6), the power is 67%.

We anticipate that 20% of the patients will not have the $\geq 50\%$ drop in tumor markers needed for study randomization arm of the study. Thus, we anticipate recruiting ~45 patients to have 36 patients for randomization.

Objective time-to-discontinuation criteria are described in Section 4.2.1. Patients may electively withdraw from treatment at any time and will be counted as a discontinuation event. All randomized patients will be included in the primary analysis. A sensitivity analysis will also be conducted, where the patients who choose to withdraw are considered as censored (non-events) at the time of withdrawal.

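### If the 12-month two-by-two comparison is kept, Fisher's exact test is needlessly conservative for the randomised 24 versus 12 patients; Boschloo's exact test would use the stated error level more fully

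*Combined protocol and SAP*

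**What the plan says.** Sections 10.1 and 10.4 size the trial for a survival-type comparison of time to discontinuation: "We plan to enroll 24 patients on the adaptive therapy and 12 on the conventional therapy arm". Section 10.1 adds "Assuming uniform enrollment of patients for 2 years", "with a minimum follow-up of 2 years, and a one-sided" alpha of 0.20, and concludes "we will have 82% power to detect a hazard ratio of 0.50, assuming 12 and 24 month median TTD". With a 20-month adaptive median the stated power is 67%. Section 10.2 repeats the main figure: "The power of the study to detect this difference is 82% for an alpha of 0.20".

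Section 10.3.1 describes a different primary analysis. "The measurement endpoint is the status of a patient 12 months following the start of TKI", scored as still on TKI or not, and the arms are compared by a Fisher's "Exact test on a two by two contingency table of patient counts based on all four combinations" of status and arm. There are two routes to that test:

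- Trial controls are first compared with historical controls. If the two do not differ at 0.1, they are pooled and the adaptive arm is tested against the pooled group.
- If they do differ, each control group is tested separately against the adaptive arm at a Bonferroni-adjusted 0.05.

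Section 10.3.1 gives neither the number of historical controls nor the sidedness of the test, does not repeat the 0.20, and does not mention that Fisher's test is conservative.

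**The concern.** Fisher's test conditions on both margins of the table. With 24 and 12 patients few p-values are attainable, so the largest one at or below the nominal level is often far below it. The real false-positive rate is then well under the rate the sponsor agreed to accept.

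A one-sided 0.20 is a deliberate trade: more false positives in return for a usable signal from 36 patients. A test that spends little more than half of that allowance gives back part of the power the allowance was meant to buy. Boschloo's test orders tables by the same Fisher p-value but sets the cut-off from the unconditional distribution. For a single comparison of two binomial groups it therefore also holds the stated level.

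**Working it through.** **Inputs.** 24 and 12 patients; one-sided 0.20; medians 12 versus 24 or 20 months; 24 months' accrual plus 24 months' minimum follow-up (10.1, 10.4); 12-month binary status, and 0.05 in the separate branch (10.3.1). Assumed: exponential times, and one-sided testing at 0.05.

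**The plan's own figure.** The probability that a patient has an event is 1 − [exp(−24λ) − exp(−48λ)]/(24λ), with λ = ln 2/median.

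- Conventional: 1 − (0.25 − 0.0625)/1.386 = 0.865, or 10.4 events among 12.
- Adaptive: 1 − (0.50 − 0.25)/0.693 = 0.639, or 15.3 events among 24. The total is 25.7.
- Standard error of the log hazard ratio: √(1/10.38 + 1/15.34) = 0.402.
- Power: Φ(0.693/0.402 − 0.842) = Φ(0.883) = 81.1%.

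A simulated log-rank test (20,000 runs) also gives 81.1%. For the 20-month scenario the two methods give 67.5% and 67.7%. The stated 82% and 67% are reproduced, for the time-to-event comparison.

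**The 12-month rates.** S(12) = 0.5^(12/median): 0.500 for a median of 12 months, 0.707 for 24 and 0.660 for 20.

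**Enumeration.** Let x of 24 adaptive and y of 12 conventional patients be on TKI at 12 months, which gives 25 × 13 = 325 tables.

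- Fisher's one-sided p is P(X ≥ x), with X hypergeometric (36 patients, x + y on TKI, 24 drawn). Reject if p ≤ α.
- Size at a common rate π is the sum over rejected tables of Bin(x; 24, π)·Bin(y; 12, π). Power uses the two arm rates instead.
- Boschloo's region is the set p ≤ c, with c the largest cut whose maximum size over π does not exceed α. For α = 0.20, c = 0.278.

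| 24 vs 12, one-sided | Fisher | Boschloo | Gain (points) |
|---|---|---|---|
| Maximum size, α = 0.20 | 0.124 | 0.196 | |
| Power, 70.7% vs 50% | 52.1% | 63.8% | 11.7 |
| Power, 66.0% vs 50% | 39.8% | 52.8% | 13.0 |
| Maximum size, α = 0.05 | 0.024 | 0.046 | |
| Power at 0.05, 70.7% vs 50% | 21.7% | 30.9% | 9.2 |

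Fisher's size at 0.20 is 0.104 for a common rate of 0.50 and 0.118 for 0.60. Boschloo's test rejects every table that Fisher's rejects, plus 11 more at 0.20 and 10 more at 0.05. If the clock starts at randomisation, about 2 months into TKI, the rates become 74.9% vs 56.1% and the gain at 0.20 is 10.4 points.

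**Choice of unconditional test.** At 70.7% vs 50% and level 0.20, a pooled-z ordering reaches 55.7% (+3.6 points) and an unpooled-z ordering 37.5%, below Fisher's. A mid-p ordering, at 62.6%, comes close to Boschloo's. The test must therefore be named.

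**Pooled branch.** With H historical controls the table is 24 versus 12 + H. H is an assumption, and pooled controls are treated as exchangeable. Gain at one-sided 0.20, 70.7% vs 50%:

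| H | 6 | 12 | 20 | 30 | 50 |
|---|---|---|---|---|---|
| Gain (points) | 8.5 | 2.0 | 9.5 | 7.9 | 5.5 |

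**Error of the two-stage rule.** Pool if the two-sided Fisher p between control groups exceeds 0.1 and test at 0.20; otherwise test the trial controls at 0.05. With 50% on TKI in both trial arms, so no true effect:

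| H | Historical rate | Fisher | Boschloo |
|---|---|---|---|
| 20 | 45% | 0.181 | 0.248 |
| 20 | 40% | 0.236 | 0.311 |
| 30 | 45% | 0.194 | 0.265 |

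**The case against.** The strongest objection is that 10.3.1 never tests 24 versus 12 at 0.20. It tests either a pooled table of unknown size or the 24 versus 12 table at 0.05, and the 0.20 belongs to the survival-type calculation. This stands. A reader might infer that the plan as written loses about 12 points of power, but the documents support that only for the randomised comparison taken alone at the sample-size alpha. In the two branches the gain is about 2 to 9.5 points (H of 6 to 50 assumed) or 9.2 points. The realised split also matters: without pooling, 25:12, 25:11 and 23:13 give gains of 9.5, 9.6 and 10.1 points.

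Second, a reader might infer that Boschloo's test keeps the same guaranteed error throughout the procedure. It does not. After a pre-test that may pool historical controls, neither test guarantees its level. A 5-point historical shortfall takes Boschloo's test above 0.20 while Fisher's stays below, so Fisher's slack gives some protection there. A 10-point shortfall takes both above.

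Third, Fisher's test is conventional and valid, and the extra power is bought with error that was permitted but unspent. That is true, and it makes this an inefficiency and not an invalid analysis. But the sponsor chose 0.20 to obtain power, and the plan gives no reason for spending less.

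Fourth, the larger problem is that the plan powers a time-to-event comparison and analyses a binary status. That also stands, and it makes this point conditional.

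**Conclusion.** The point holds for the comparison of randomised adaptive with randomised conventional patients, if the two-by-two analysis is kept. Fisher's test there uses at most 0.124 of a one-sided 0.20, and Boschloo's test gains 11.7 points of power under the plan's main scenario and 13.0 under its second. At one-sided 0.05 the gain is 9.2 points. These figures rest on a 24:12 split, exponential times and, at 0.05, one-sided testing.

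The error guarantee is limited to that randomised comparison and does not extend to tables pooled with historical controls. Nor should the change be read as rescuing the stated power: 82 − 63.8 leaves about 18 points, because the 82% belongs to the time-to-event comparison.

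**What to change.** If the binary analysis is kept, amend 10.3.1 before any outcome data are seen:

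- Name Boschloo's unconditional exact test for the comparison of randomised adaptive with randomised conventional patients in the proportion on TKI at 12 months. Fisher's p-value can stay as a supportive figure.
- State that the test is one-sided, and at what level.
- Replace the 82% by that test's own power. At 0.20 this is 63.8% for 70.7% vs 50% and 52.8% for 66.0% vs 50%; at 0.05 it is 30.9% for the first scenario.
- Claim control of the error rate for this randomised comparison only, and say that no level is guaranteed for a table pooled with historical controls.

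The cost is a few sentences; the test is in standard software, and no extra patients or data are needed. The downside is that Fisher's slack is spent: the maximum false-positive rate at nominal 0.20 rises from 0.124 to 0.196, still within the stated level. If the primary analysis is realigned to the time-to-event comparison behind the 82%, the change is unnecessary.
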